#### **How to use & store your aroma inhaler\***

##### **DIRECTIONS: To use 3 times daily and as desired:**

###### 1. Uncap Inhaler

Hold within 3 inches of the nose

###### 2. Gently breath in through your nose and hold for 3 seconds, gently exhale through your mouth

Repeat 3 times each day and as desired (Use the comments section of the logbook to record extra use and thoughts about using your aroma inhaler)

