## Study Duration (7 days)

## Study Time Involved for Participants

Time involved in completing prescreening, informational session, & pre-surveys

	Step	What is happening	Who does what	Approximately how much time to expect
1	Prescreening	6 question survey	Administered by Enroller	2-3 minutes
2	Open packet & review contents Complete CONSENT	Looking at contents of packets	Enroller reviews consent & participant will either sign or decline	5-10 minutes
2a	Trying out aroma inhaler & giving directions for use	Participant opening their own aroma inhaler	Participant opens aroma inhaler. Enroller demonstrates correct use using their own inhaler	1-2 minutes
2b	Personalizing packet for each participant	Adding dates and organizing packet, going	Enroller adds dates with participant	2-4 minutes

		over logbook together	involvement. Enroller explains follow up texts or emails that participant will begin receiving the next day.	
3	Complete 3 pre-surveys	69 questions (28 GCQ, 20 Ease, 21 DASS)	Participant does this and then they are excused	5-6 minutes
			TOTAL	

More time can be taken to complete these steps and participants may request to meet with the Enroller again if they still have questions.

Time involved in study activities from day 1 to day 7 and completing post-surveys

	Step	What is happening	Who does what & extra details	Approximately how much time to expect
1	Using aroma inhaler 3 x day x 7 days	Participant inhales aroma from inhaler for approximately 1 minute on 3 separate occasions during each day of the study	Participant is responsible. Reminders are sent via text or email during the first 3 days of the study. This reminder should not add any extra time to the study	21 minutes
2 Intervention	Filling out daily logbook x 7 days	Participant puts an X or check mark next to the 3 spaces to document use of aroma inhaler. Also, at the end of the participant's day, Comfort is rated on a 0-10 VAS.	Participant is responsible. A place for comments is available and participants may take their time to add comments about the day (this is discretionary)	7-10 minutes

2 Control	Filling out daily logbook x 7 days	At the end of the participant's day, Comfort is rated on a 0-10 VAS.	Participant is responsible. A place for comments is available and participants may take their time to add comments about the day (this is discretionary)	Same as Intervention group

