**Use of the Aethereo®Stick is reviewed (Appendix B for details about inhaler):**

- a. Enroller will either open or have participant open the sealed package for the Aethereo®Stick (aroma inhaler) open the outer sealed package
- b. Save the package for storage
- c. Pick up the inhaler and twist to the right to remove the cap
- d. There is no need to shake the inhaler
- e. Breath out gently
- f. While holding the inhaler about 3 inches (7.62 cm) from the nose
- g. Inhale through the nose using 3 sniffs as directed
- h. Hold breath for about 3 seconds
- i. Exhale for 3 seconds
- j. Repeat 3 times and then recap and store the inhaler in a safe place away from high heat and direct sunlight, children, and pets.
- k. NOTE: The Enroller will record all reactions to participant exposure to the aroma inhaler. Verbatim recording of any negative or positive response is vital. This is recorded on the Prescreening survey at the bottom of the form. Any negative or adverse reaction must be recorded. If no negative reaction, then the Enroller must write, "No negative reaction"

9. As needed use:

- a. The inhaler may be used more than 3 x daily
- b. Participants may use as needed and are asked to record all uses and reasons for uses in the provided logbook

10. Use other than instructed:

- a. If the participant uses the inhaler in some other fashion than instructed, they are asked to record this information as well (i.e. inhales x 10, inserts into nostril [which is considered safe], uses a different count to exhale etc.)

11. How Participant begins intervention:

- a. The participant begins the 7-day intervention at the beginning of their next full day of life (This allows for those who work nights etc.)
  - i. ADD DATES: Participants (preferable to have participants do this and not the Enroller) will add dates to pages of the logbook (e.g., If they received their packet and instructions on October 11, then they should begin their study on the NEXT FULL DAY, October 12, and their study would be

complete on October 18. Dates on pages should reflect the 7-days of the study, 10/12, 10/13 and so forth to 10/18)

- b. Three times daily means spaced out in 3 times, which could mean morning, afternoon, and evening, or anything else that is separated by approximately 4-6 hours (while awake)

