### How do you use an AethereoStick?

Unscrew the outer cap. Hold the AethereoStick a few inches from your nose and take three or four slow, deep breaths. Enjoy. Repeat as desired.

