**AROMA INHALER STUDY**

**LOGBOOK**

**INTERVENTION GROUP**

**Directions for using your aroma inhaler and this logbook:**

**Follow these steps to use your aroma inhaler:**

1. Hold the aroma inhaler by the base
2. Twist off the cap. The inner part of the aroma inhaler with the essential oil-soaked cotton wick is part of a closed system and is not intended to be opened. All you need to do is twist off the cap
3. Hold the aroma inhaler within 3 inches of your nose
4. Breath in gently through your nose for 3 seconds
5. Hold your breath for about three seconds and then exhale gently through your mouth
6. Repeat this 3 times\* and then replace the cap and store your aroma inhaler in a cool, dry place away from children or pets. (You may repeat this breathing cycle more than 3 times each day, please remember to make a note of this in the comments section about when and why you did)
7. Use at least 3 times a day, and if you want to, use it more, but this should be recorded on the daily logbook page

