## Appendix E

### Reminder Paper

#### SEVEN DAY AROMA INHALER STUDY

(Please post this in a place where you will see it each day as a reminder to use your aroma inhaler and logbook) **Thank you for your participation ☺**

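### The posted Reminder paper gives no breath count per use and can be read as 3 breath cycles a day, where the logbook and manual direct at least 9

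*Combined protocol and SAP*

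**What the plan says.** Three participant documents and two parts of the manual describe how to use the inhaler.

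- **Reminder paper (Appendix E).** Participants are told: "Please post this in a place where you will see it each day". The directions are headed "To use 3 times daily and as desired". Step 1 is to uncap. Step 2 describes a single breath in, a 3-second hold and a breath out, followed by "Repeat 3 times each day and as desired". Step 3 is to recap and record. No step gives a number of breaths per use.
- **Intervention logbook directions (Appendix D).** Steps 4 to 6 describe the same cycle, to be repeated 3 times before the cap goes back on. Step 7 says "Use at least 3 times a day, and if you want to, use it more". The bracket in step 6 says "You may repeat this breathing cycle more than 3 times each day", which counts cycles where it seems to mean uses.
- **Manual, section on reviewing use of the Aethereo Stick.** After the inhale, hold and exhale steps, step j says "Repeat 3 times and then recap and store the inhaler in a safe place". Item 11b defines three times daily as three occasions about 4 to 6 hours apart.
- **Product information sheet (Appendix B), left in the intervention packet.** It tells the user to "take three or four slow, deep breaths".
- **Study Time Involved for Participants.** The planning table says "Participant inhales aroma from inhaler for approximately 1 minute on 3 separate occasions during each day of the study", for a total of 21 minutes.

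**The concern.** In the logbook and the manual, the repeat instruction belongs to a single use: three cycles, then recap. On the Reminder paper the same number is attached to the day. The heading also counts per day, so a participant can take the sheet to mean one breath cycle, three times a day. Of the three participant documents that explain inhaler use, it is the only one with no per-use count.

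Two features give this some weight. First, it is the sheet meant to be on display all week. Reminder messages are planned for days 1 to 3 and day 7, so on days 4 to 6 no message is sent. Second, the logbook boxes record whether the inhaler was used as directed a first, second and third time. They do not record cycles. The Statistical Analysis Plan takes Aim 2b adherence from the logbook entries, so someone doing one cycle per use could tick every box in good faith and count as fully adherent. Intervention fidelity is a named part of Aim 2.

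**Working it through.** **The plan's own figure.** The time table's total reproduces: 1 minute × 3 occasions × 7 days = 21 minutes. This confirms that the plan counts dose as three occasions a day.

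**Inputs for the cycle count**

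| Source | Cycles per use | Uses per day |
|---|---|---|
| Reminder paper, literal reading | 1 | 3 |
| Reminder paper, alternative reading | 3 | 3 |
| Logbook steps 4–7 | 3 | at least 3 |
| Manual steps g–j and item 11b | 3 | 3 |

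**Cycles per day = cycles per use × uses per day; over the study, × 7**

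- Reminder paper, literal: 1 × 3 = 3 a day; 3 × 7 = 21.
- Logbook and manual: 3 × 3 = 9 a day; 9 × 7 = 63.
- Ratio: 21 / 63 = 33%.
- Reminder paper, alternative: 3 × 3 = 9 a day, so no shortfall.

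**Sensitivity to the word repeat.** If repeating 3 times means three further cycles after the first:

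- Reminder paper, literal: 1 + 3 = 4 a day; 4 × 7 = 28.
- Logbook and manual: (1 + 3) × 3 = 12 a day; 12 × 7 = 84.
- Ratio: 28 / 84 = 33%.

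The ratio is the same as long as the word is read the same way on both sheets.

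**Timing comparison.** Take a 3-second breath in (logbook step 4), a 3-second hold (logbook and manual) and a 3-second breath out (manual step i).

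- One cycle: 3 + 3 + 3 = 9 s; 9 / 60 = 15% of the planned minute.
- Three cycles: 27 s; 27 / 60 = 45%.
- Four cycles: 36 s; 36 / 60 = 60%.

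The single-cycle reading is furthest from the planned duration. Correct use also falls short of a minute, and the minute may include uncapping, pauses and recapping (an assumption). The comparison therefore shows which reading fits the plan better and does not measure lost dose.

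**The case against.** The strongest reply is that the Reminder paper only prompts people who have already been trained. The Risk and Safety Monitoring sections say participants demonstrate correct use back to the researcher. Under the mailed procedure in Appendix G, a further meeting or call follows receipt of the materials. The logbook and the product sheet both indicate several breaths per use. To under-dose, a participant would have to let the posted sheet override all of these. This stands as a reason to think the misreading uncommon, but it does not make the sheet clear. The logbook is not a clean safeguard either, because its step 6 bracket mixes cycles with uses.

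A second reply is that item 10 of the manual asks participants to record any use that differs from the instructions, including a different number of inhalations, and the logbook has daily comment fields. This is a partial safeguard: someone who believes one cycle is correct has no deviation to report.

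A third is that the protocol sets dose in uses and never states a daily number of cycles, that extra use is allowed, and that the content of a breath varies (three sniffs in the manual, a 3-second breath in the logbook). This is fair as far as it goes. The 9 a day is derived from the per-use and per-day instructions and is not a stated target, so 33% compares two readings of the instructions and does not estimate dose lost.

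Finally, changing the wording once enrolment has begun leaves two instruction versions in the intervention arm. That is a real but small cost.

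**Conclusion.** The concern holds, as a minor point. The Reminder paper's use instruction departs from the logbook and manual and can reasonably be read as 3 cycles a day where they direct at least 9. On that reading a participant does 33% of the directed minimum; on the three-cycles-at-three-uses reading there is no shortfall. The documents do not indicate how many participants would take the literal reading, so no expected effect on dose or outcome is claimed.

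The consequence is limited to consistency of the intervention and to what Aim 2b adherence can detect. All the sheets agree on three uses a day. The sample size, the planned tests and the randomised comparison are unchanged.

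The result assumes that a cycle means one inhale, hold and exhale, that the manual's sniffs and the logbook's breath count as the same unit, and that repeat is read alike on both sheets.

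**What to change.** 1. **Reminder paper, step 2.** Replace the repeat sentence with: *Repeat this breath 3 times at each use; use at least 3 times each day, and more if desired.*
2. **Intervention logbook, step 6 bracket.** Refer to more than 3 uses a day, not to repeats of the breathing cycle.
3. **If enrolment is under way,** record the date of the change so that participants can be classified by the instruction version they received.

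The cost is two wording edits, a reprint of the Reminder paper and the intervention logbook directions, and a minor IRB amendment. The logged updates run to an approval on 2/5/2024, so enrolment may already have begun. In that case the intervention arm would contain two instruction versions, which the recorded date makes identifiable. The design, sample size, analysis and data collected stay as they are.

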###### 3. Recap Inhaler & Record all uses & reactions to the inhaler in the Logbook\*\*

###### 4. Keep your aroma inhaler and logbook in a safe place. The aroma inhaler is yours to keep.

\*\*The logbook is returned at the end of this study

\*(When not in use, recap to close & store in a cool, dry place away from children and pets) It is OKAY to keep your closed inhaler in your pocket or purse and at room temperature ☺

Do not tamper with the packaging. Keep out of reach of children and animals. If you develop any adverse reactions such as a headache, stop, recap inhaler, and retry a little later. If

OFFICE OF HUMAN RESEARCH PROTECTION

unpleasant effects, such as headache continue, discontinue use and contact [name],

Investigator at [[contact]](mailto:[contact])

Thank you!

## PROTOCOL MANUAL: AROMATHERAPY & SUD

Appendix G (IRB Update allowing Stages one, two, three, and peer recovery recruitment)

# PROTOCOL MANUAL: AROMATHERAPY & SUD

## Approval of Protocol Amendment

---

09/26/2022

**To:** [name]

**From:** WVU Office of Human Research Protections

**Protocol Type:** Expedited

**Approval Date:** 09/26/2022

**Submission Type:** Amendment

**Expiration Date:** 07/28/2023

**Funding:** N/A

**WVU Protocol #:** 2204562633A002

**Protocol Title:** Using Aromatherapy for Comfort, Ease, and Stress for Adults being Treated for Substance Use Disorder in North Central Appalachia: A Randomized Controlled Trial

---

The West Virginia University Institutional Review Board has reviewed your request for modifications to the Expedited protocol 2204562633A002, in accordance with 45 CFR 46, 21 CFR 50, and 21 CFR 56 (when applicable). The amendment wording is as follows:

- Amendment wording: During a Zoom meeting between the enroller (study personnel) and the participant, the following changes include: Consent form amended to delete an item of data collection (p. 3, #11, presence of severe mental illness, will not be collected), pre-surveys are done online, given by Qualtrics: Comfort, Ease, and Stress. A demographic data collection form has been submitted as an attachment for clarity on self-report and chart data collected (this is not added to the study packets for participants). All study materials will be mailed to participants instead of in-person enrollment. The initial prescreening of sniffing the bergamot aroma inhaler will occur in the participant's home. Once the participants receive their study materials in the mail, another meeting or phone call will be done between the participant and the enroller (study personnel). In addition, the recruitment population has been widened to include all phases of treatment, including peer recovery coach program (all part of West Virginia University Chestnut Ridge Center (WVUCRC)

The following documents were reviewed and approved for use as part of this submission. Only the documents listed below may be used in the research. Please access and print the files in the Notes & Attachments section of your approved protocol.

Protocol #: 2204562633A002  
FWA: 00005078

[contact]  
[contact]

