## Research Summary

### Updates to Study Protocol

Update: IRB amendment 09262022 (Appendix G)

To allow Stages one, two, and three and peer recovery persons to participate.

Update: IRB Amendment 08312022 (Appendix H)

To recruit and consent participants online

Update: From QIP Audit 10252022 (Appendix I)

Annual Review with approval received 7/29/2023

8/23/2023 Per email communication with co-I [name], BMed no longer using site approval forms. I have approval to proceed with recruitment when IRB approval is obtained.

Update to consent process 8/2023 (completed)

Communication with participants, begin using RedCap WVU for all surveys and emails. WVU phone and computer for all communication.

10/23/2023 Update: Will no longer include copy of consent in study packets mailed to participants. This will save on mailing costs. Participants can download and print or save to their devices. Approved 11/7/2023

11/21/23 Submitted amendment re: addition of [name] and [name] CITI training certificates to the protocol

12/27/23 Amendment to add a population from Health Right, approved 2/5/2024

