## Statistical Analysis Plan

Data analysis For Aim 1, Descriptive (frequencies, means, ranges, standard deviations) and bivariate analysis will be conducted on the demographics, GCQ, Ease measure, and DASS scales. Statistical assumptions (i.e., normal distribution and homogeneity of variances etc.) will be tested. Sample demographics of patients will be reported. Fisher's exact test will be used for categorical variables; Repeated measures ANOVA and paired t-test will be used for continuous variables. Pearson's and Spearman's correlation analyses will be used to explore relationships among variables (Pallant, 2020). The statistical significance is set at a 5% (alpha = 5%). All analyses will be completed using Statistical Package for the Social Sciences (IBM SPSS).

For Aim 2, Descriptive statistics will be used to analyze Aim 2a. Participant recruitment, enrollment, and retention rates will be tabulated and reported. Reasons for non-participation and attrition will be recorded and will be used to develop strategies to address this. For Aim 2b, adherence to the intervention protocol will be calculated from responses in the logbooks. For Aim 2c, to determine the cost of the intervention implementation, all charges related to implementation are calculated. This includes costs of personnel time for administering each session, the materials, and incentives.

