## Sample Size

Sample size was calculated using G\*Power v.3.1.9.7 on repeated measure ANOVA given  $\alpha=0.05$ , moderate effect size (0.25), power of 80%, two groups with 2 measurements, correlation among repeated measures (0.50), a total sample size of 98 will be required. A total sample size of n=49 for intervention group and n=49 for control group is sought.

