### **Plus, the following**

#### **Data will be collected from the chart and from survey (self-report)**

1. Identifier variables of Comfort, Ease, and Stress
2. Stage of treatment in the SUD treatment program (Chart)
3. Presence of anxiety and/or depression (Chart)
4. Presence of severe mental illness Dx (Chart)
5. Allergies to citrus fruits such as grapefruit, lemon, orange, or bergamot (Chart and self report)

6. Previous experience with any integrative or complementary therapies such as yoga, massage, acupuncture, aromatherapy with essential oils, herbal preparations, meditation, mindfulness practices (Self-report)
7. Pregnant and/or nursing (Self-report)
8. Severe breathing problems such as asthma, chronic bronchitis, or COPD (Chart and self-report)
9. Report of sense of smell (self-report)
10. Dx of a problem with sense of smell (Chart and self-report)
11. Current illness with cold, flu, or covid (Self-report)

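### Recruitment was widened to all treatment phases, peer recovery and a Health Right population, but the between-arm comparison names no covariate, although treatment stage is collected; the cost is modest precision, not validity.

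*Combined protocol and SAP*

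**What the plan says.** The Study Population section and the eligibility list under Prior to opening a Study Packet describe people at one centre who have finished intensive phase 1. The approved amendment in Appendix G says that "the recruitment population has been widened to include all phases of treatment, including peer recovery coach program"; it places all of these within the same centre. Updates to Study Protocol lists that change and a further one: "12/27/23 Amendment to add a population from Health Right, approved 2/5/2024".

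Eligible people receive the next packet from a single sequence, 001 to 098. No stratification by stage or source is described.

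The chart items to be collected include "Stage of treatment in the SUD treatment program (Chart". Recruitment source is not in the list of data items.

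For Aim 1 the Statistical Analysis Plan states: "Repeated measures ANOVA and paired t-test will be used for continuous variables". It also plans Fisher's exact test, descriptive and bivariate analysis of demographics and the three scales, and correlations among variables it does not list. It names no covariate, stratum or subgroup, and does not say which ANOVA term tests Hypotheses 1a and 1b.

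Sample Size gives "moderate effect size (0.25), power of 80%, two groups with 2 measurements" and "correlation among repeated measures (0.50), a total sample size of 98 will be required".

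**The concern.** The enrolled group can now include people in stage one, people in later stages, people in peer recovery, and people from another source. If these groups change differently over a week, and the comparison ignores this, that variation stays in the error term. In a trial of 98 the arms can also differ by chance in their share of early-stage people, and the estimate then moves with that difference.

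Stage is fixed before allocation and already collected, so using it costs little. If it is left out of the plan, any later decision to adjust would be taken after the arms had been compared, and would be open to the charge of being data-driven.

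**Working it through.** **Inputs from the documents.** f = 0.25 (d = 0.5 for two groups), 5% significance, power 80%, two measurements with correlation ρ = 0.50, N = 98, 49 per arm.

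**Assumptions (not in the documents).** 30% of participants are early-stage. Early stage shifts the post score by g SD beyond what the baseline score predicts. All 98 complete.

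**1. The plan's own figure.** For the between-groups term of a repeated measures ANOVA, λ = N·m·f²/(1 + (m − 1)ρ) = 98 × 2 × 0.0625/1.5 = 8.167 on 1 and 96 df. Power is 0.808; N = 96 gives 0.799. So 98 reproduces. The group-by-time formula, λ = N·m·f²/(1 − ρ), would need only N = 34, so 98 matches the between-groups term alone.

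**2. Effect of baseline adjustment.** Take a true post-test difference of 0.5 SD.
- Group-by-time test: the variance of a change score is 2(1 − ρ) = 1. λ = (49/2) × 0.25/1 = 6.125; power 0.688.
- Post score adjusted for baseline: residual variance 1 − ρ² = 0.75. λ = 6.125/0.75 = 8.167; power 0.808. At ρ = 0.5 this λ happens to equal the one in step 1.

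**3. Effect of adding stage to the baseline-adjusted model.** Leaving stage out raises the residual variance to 0.75 + g² × 0.3 × 0.7. Without stage, λ = 6.125 divided by that variance (95 df). With stage, λ = 6.125/0.75 = 8.167 (94 df).

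| g (SD) | Residual variance without stage | λ without stage | Power without | Power with |
|---|---|---|---|---|
| 0 | 0.7500 | 8.167 | 0.8075 | 0.8074 |
| 0.2 | 0.7584 | 8.076 | 0.803 | 0.807 |
| 0.3 | 0.7689 | 7.966 | 0.798 | 0.807 |
| 0.5 | 0.8025 | 7.632 | 0.781 | 0.807 |
| 0.8 | 0.8844 | 6.926 | 0.741 | 0.807 |

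The last column takes the arms as balanced on stage. Counting degrees of freedom alone, a non-prognostic stage term costs less than 0.1 point. Stage and arm will also be slightly associated by chance (expected squared correlation 1/97). That lowers λ to 8.167 × 96/97 = 8.08 and the adjusted power to about 0.803. On that stricter count the cost at g = 0 is about 0.4 point, the gain at 0.2 SD disappears, and the gains at 0.5 and 0.8 SD are about 2 and 6 points.

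**4. Chance imbalance.** The SD of the between-arm difference in early-stage share is √(0.3 × 0.7 × 4/98) = 0.093. A difference of 1.96 × 0.093 = 0.18, that is 18 percentage points, or more occurs in about 1 trial in 20. At g = 0.5 the typical (mean absolute) shift of the estimate is 0.5 × 0.093 × √(2/π) = 0.037 SD. The 1-in-20 shift is 0.5 × 0.18 = 0.09 SD or more.

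**5. Steps 3 and 4 are the same variance.** The standard error with stage in the model is √(0.75 × 4/98) = 0.175. Adding the imbalance variation gives √(0.175² + (0.5 × 0.093)²) = 0.181, which equals √(0.8025 × 4/98), the standard error without stage.

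**The case against.** Randomisation keeps the unadjusted comparison valid, and this is a pilot. Adjustment is an optional gain that depends on a prognostic strength no document supplies. All of that stands: at 0.2 SD or below there is nothing to gain.

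The sample size rests on a generic standardised effect. If the planned total variance already includes stage differences, the unadjusted analysis keeps 0.808 and adjustment at 0.5 SD raises it to 0.835. On that reading stage adjustment is a bonus, not a repair. The documents do not settle which reading applies; the gain is about the same on either.

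If Hypotheses 1a and 1b are tested by group-by-time, stable differences in level between stages cancel already. Only differences in how people change remain. This also stands, and it is why g is defined here as a shift beyond baseline.

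A reader might infer more than the text allows:
- *That chance imbalance biases the result in addition to the lost precision.* Step 5 shows they are one quantity. It is not bias over repeated randomisation, and type I error is unaffected.
- *That stage is used nowhere.* The demographic summaries or the correlations could include it, and Appendix G mentions a demographic form that is not shown. Neither would adjust the treatment comparison, though, and stage is not named.
- *That a second clinic was added.* The update speaks only of a population from Health Right.
- *That stage is available for everyone.* The data list does not say so; people from peer recovery or Health Right may have no stage in this programme.

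**Conclusion.** The point holds as one of efficiency. Recruitment was widened, no stratified allocation is described, and the between-arm comparison names no covariate, although a relevant pre-allocation variable is listed for collection. Under the stated assumptions (30% early-stage, 98 completers, 0.5 SD effect, ρ = 0.5), adding stage to a baseline-adjusted model is worth nothing at a 0.2 SD shift, about 2 to 3 power points at 0.5 SD and 6 to 7 at 0.8 SD. It costs less than half a point if stage is irrelevant. At 0.5 SD the typical imbalance shift is about 7% of the target effect (0.037/0.5).

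Baseline adjustment matters more: it moves power from 0.688 to 0.808 relative to a group-by-time test. Whether the plan forgoes that gain cannot be settled, because the tested term is not named.

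Separately, the two eligibility sections that require completion of phase 1 contradict the amendment that admits all phases.

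**What to change.** In the Statistical Analysis Plan, prespecify the between-arm model for comfort, ease and stress as the post score on arm, with its own baseline score and treatment stage (stage one versus later) as covariates. Give people with no programme stage their own category.

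Add recruitment source (Chestnut Ridge treatment programme, peer recovery, Health Right) to the data items as a separate variable. Stage and source should not be merged into one factor, because a person from Health Right may also be early-stage. Tabulate both by arm.

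Reconcile Study Population and Prior to opening a Study Packet with Updates to Study Protocol and Appendix G on which phases are eligible.

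The cost is a short addition to the plan, a few degrees of freedom and one extra data field.
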